## 6.9 Withdrawal from the Study

Patients have the right to discontinue study treatment any time for any reason, without prejudice to their medical care. Withdrawal from the study refers to discontinuation of both study medication and study assessments; this can occur at any time according to the following reasons:

- Patient decision
- Lost to follow-up
- Death
- PI decision

Patients may withdraw consent at any time for any reason or have trial treatment stopped at the discretion of the investigator should any untoward effect occur. In addition, a patient may be withdrawn by the investigator or the Sponsor if enrolment into the trial is inappropriate, the trial plan is violated, or for administrative and/or other safety reasons. When a patient discontinues/withdraws prior to trial completion, all applicable activities scheduled for the final trial visit should be performed at the time of discontinuation, these are listed in the schedule of study assessments (Table 3). Any AEs which are present at that time should be followed in accordance with the safety requirements outlined in Section 7.

Patients who a) attain a complete response or b) complete 24 months of treatment with pembrolizumab may discontinue treatment with the option of restarting treatment on disease progression. Retreatment should be discussed with the Chief Investigator. Study related assessment and procedures should be as for the beyond Pembrolizumab Maintenance phase (see Table 3). Patients do not need to re-sign the consent form for restarting treatment, provided their consent is on the most up-to-date version of the Patient Information Sheet Consent Form. After discontinuing treatment following assessment of complete response, these

patients should return to the site for a 30 days safety follow-up visit and then proceed to the follow-up period of the study.

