#### **3.4.3 Survival Status Follow-Up Phase**

Once a patient experiences confirmed disease progression or starts a new anti-cancer therapy, the patient moves into the survival follow-up phase and will be followed up every 12 weeks to determine their disease status. This will be done by reviewing their medical notes and / or contacting the patient or GP directly. Patients will remain on this follow-up until death, withdrawal of consent, or the end of the study, whichever occurs first.

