### 4.3 Patient Replacement Strategy

Additional patients may be enrolled in a given cohort to ensure that the required number of evaluable patients in each cohort is achieved. A patient that discontinues the trial for progressive disease within 3 months of the last dose of radiotherapy will not be evaluable for DLTs and therefore will need to be replaced. A patient that discontinues the trial for a drug-related AE will not be replaced and will be counted in the evaluable population of patients for the respective cohort. However, patients found to have active

pneumonitis on C1D1 of pembrolizumab or day 1 of radiotherapy will be removed from the trial and can be replaced. Also patients who do not reach follow-up 3 months post completion of lung SBRT for reasons other than progression or toxicity can be replaced by new patients in that cohort to ensure there is a minimum of 3 (or 6 if required) patients in each cohort.

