### **6.8 Permanent Discontinuation of Trial Medication and Withdrawal from the Study**

#### **6.8.1 Permanent Discontinuation of Trial Medication**

A patient may be permanently discontinued from the trial medication for any of the following reasons:

- The subject withdraws consent.
- Confirmed radiographic disease progression, please see Section 6.3.11.4.

*Note:* For unconfirmed radiographic disease progression. A patient may be granted an exception to continue on treatment with confirmed radiographic progression if clinically stable or clinically improved.

- Unacceptable adverse experiences
- Intercurrent illness that prevents further administration of treatment
- The patient has a confirmed positive serum pregnancy test
- Noncompliance with trial treatment or procedure requirements
- Administrative reasons
- Completion of 24 months of pembrolizumab

Trial patients will not be enrolled more than once. The primary reason for discontinuation should be recorded on the CRF. Once the trial medication has been discontinued the patient should complete the end of treatment (if applicable) and safety follow-up visit procedures as listed in the schedule of study

assessment (Table 3). After the end of treatment, patients will continue to be assessed for AE and SAE monitoring until completion of the safety follow up visit.

Follow-up actions for patient discontinuing the trial are as follows:

- All patients will be required to:
  - Attend a safety follow-up 30 days after their last dose of pembrolizumab,
- If a patient **progresses or begins a new anti-cancer treatment** they will be required to:
  - Undertake survival status assessments every 12 weeks until death, withdrawal of consent, lost to follow up or the end of the study.
- If a patient discontinues for reasons other than progression during treatment and **does not withdraw their consent to follow up** they will be required to:
  - Attend follow-up assessments every 9 weeks until disease progression, initiation of a new anti-cancer treatment death, end of the study. Information regarding post-study anti-cancer treatment will be collected if new treatment is initiated.

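### Section 6.9 lets the investigator or Sponsor end a consenting patient's further scheduled assessments, where 6.8.1 and 3.4.3 keep such patients in follow-up; PFS and OS could be informatively censored

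*Combined protocol and SAP*

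**What the plan says.** Section 6.9 gives the definition: "Withdrawal from the study refers to discontinuation of both study medication and study assessments". PI decision is one of its listed reasons, and the text adds that "a patient may be withdrawn by the investigator or the Sponsor if enrolment into the trial is inappropriate, the trial plan is violated", with the list continuing "the trial plan is violated, or for administrative and/or other safety reasons". None of these grounds requires the patient to withdraw consent.

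Some things continue after a 6.9 withdrawal: "all applicable activities scheduled for the final trial visit should be performed at the time of discontinuation", and "Any AEs which are present at that time should be followed in accordance with the safety requirements outlined in Section 7".

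Section 6.8.1 deals with stopping trial medication. Its reasons overlap with those of 6.9: "Noncompliance with trial treatment or procedure requirements", administrative reasons and unacceptable adverse experiences. It requires a 30-day safety visit for all patients. Those who stop without progression and have not withdrawn consent to follow-up are then seen every 9 weeks. Those who progress or start new therapy have survival contact every 12 weeks.

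Section 3.4.3, on the survival phase, says: "Patients will remain on this follow-up until death, withdrawal of consent, or the end of the study, whichever occurs first".

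Section 4.3 counts a patient who leaves for a drug-related AE as evaluable and does not replace that patient. It also says that "patients who do not reach follow-up 3 months post completion of lung SBRT for reasons other than progression or toxicity can be replaced".

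Section 8.1.2 censors PFS and OS at the date of last follow-up for surviving patients. It has no rule for a withdrawal made by the investigator or Sponsor.

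**The concern.** A consenting patient who breaks the protocol, or whose treatment is ended for administrative or safety reasons, has two possible fates. Under 6.8.1 the patient stays in follow-up. Under 6.9 the same patient may leave all further scheduled assessment. The choice falls to staff who know the patient's condition, since the trial is open label (6.2.8).

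Kaplan-Meier estimation assumes that a censored patient has the same outlook as those still at risk. A withdrawal on safety grounds or by PI decision may well be related to prognosis. If the patients withdrawn are those about to progress or die, the 6- and 12-month PFS and OS named in 2.2.2 will be too high. With at most 24 patients, one or two such cases are visible in the estimate.

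**Working it through.** **1. Size of the trial.** Two dose levels of 3 to 6 patients give 2 × 3 = 6 to 2 × 6 = 12. Adding 12 in expansion gives a maximum of 24, as 8.2 and 3.1 state. There is no alpha, power or dropout figure to reproduce, and no expected withdrawal rate.

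**2. The rules side by side.**

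| Section | Who or what it covers | What can end follow-up |
|---|---|---|
| 6.9 | Any patient, at any time | Patient decision, loss to follow-up, death, PI decision; investigator or Sponsor for inappropriate enrolment, violation, administrative or other safety reasons |
| 6.8.1 | Stopped drug without progression | Progression, new therapy, death, end of study, or withdrawal of consent to follow-up |
| 6.8.1 | Progressed or on new therapy | Death, withdrawal of consent, loss to follow-up, end of study |
| 3.4.3 | Progressed or on new therapy | Death, withdrawal of consent, end of study |
| 5.3.11.2 | Tumour imaging | Progression, new therapy, withdrawal of consent, death, end of study |

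Non-compliance or violation, administrative reasons and safety appear in both 6.8.1 and 6.9, with different consequences for follow-up. Only 6.9 lets the investigator or Sponsor end it.

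**3. What is lost.** After a 6.9 withdrawal there is no further scheduled imaging, survival contact or toxicity assessment to the end of the DLT window, which is 12 weeks from the last SBRT dose (3.2).

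**4. Illustration for 12-month OS.** Assumptions: 24 patients; exponential OS with a median of 10.4 months (the figure in 1.1.4.2 for previously treated patients in KEYNOTE-001), taken here from the start of radiotherapy; administrative censoring at 24 months. In addition, k patients who would die within 12 months are censored one month before death. The values of k are assumed.

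- True 12-month OS = exp(−ln 2 × 12 / 10.4) = 0.449.
- Sampling SD with complete 12-month follow-up = √(0.449 × 0.551 / 24) = 0.10.
- Mean Kaplan-Meier estimate at 12 months over 20,000 simulated trials:

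| k | 0 | 1 | 2 | 3 |
|---|---|---|---|---|
| Estimate | 44.9% | 47.6% | 50.3% | 53.3% |

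That is about 3 points per patient (2.7, 2.7 and 3.0). A hand check agrees. Kaplan-Meier passes a censored patient's weight of 1/24 to those still at risk. The shift is therefore about 0.449/24 = 1.9 points for someone withdrawn at the start, and approaches 1/24 = 4.2 points for someone withdrawn close to month 12.

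**5. Bounds without a survival model.** Each patient withdrawn alive with unknown 12-month status widens the best-to-worst-case range by 1/24 = 4.2 points; three patients widen it by 3/24 = 12.5 points.

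**6. DLT evaluability.** Section 4.3 keeps drug-related AE leavers in the evaluable set, and its clause on other reasons excludes toxicity. What remains is the patient withdrawn for a violation, an administrative reason or by PI decision before the window closes. That patient can be replaced, and under 8.1 is described separately as having incomplete safety observation. One unseen DLT could turn 2/6 (maximum administered dose reached) into 1/6 (escalate), but it must fall in this narrow group.

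**The case against.** The strongest reply is that 6.8 and 6.9 describe different states, stopping drug and leaving the study, and that 6.9 is only permissive. Several parts of it stand.

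- Withdrawal does not end all observation. Final-visit procedures and follow-up of existing AEs remain under 6.9. Section 6.8.1 asks all patients to attend the 30-day safety visit. Section 7.4.1 requires SAE reporting to that visit or new therapy, and reporting of related SAEs that come to light outside that period.
- Section 3.4.3 covers only patients who have progressed or started new therapy, and its list is not exhaustive: it omits loss to follow-up, which 6.8.1 includes. Section 3.4.2 ends disease follow-up at withdrawal without saying whose decision that is. The firm conflict is therefore the shared grounds in 6.8.1 and 6.9.
- Inappropriate enrolment and administrative reasons need not be related to outcome, and deterioration is not a listed ground.
- OS is a secondary endpoint with no hypothesis or decision threshold, and a 3-point shift is small beside an SD of 10 points.

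A reader might infer that 6.9 seriously weakens the escalation rule. The chance of clearing a level is (1−p)³ + 3p(1−p)⁵. If a share w of would-be DLT patients leave unseen and are replaced, p becomes p(1−w)/(1−pw). At p = 0.30 the chance is 49.4% for w = 0 and 53.9%, 58.8% and 64.2% for w = 10%, 20% and 30%. The documents give no basis for any such w. Section 4.3 blocks the most obvious route, and the Safety Review Committee, with an independent chair, reviews each cohort's toxicity before escalation (3.2, 10.9). These figures show direction only.

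A reader might also infer that ORR and DCR are inflated. They are not: 8.1.2 divides by all treated, so a withdrawn patient stays in the denominator and missing later scans can only lower the rates.

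None of this settles which section governs a consenting patient, or supplies the missing imaging and survival data.

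**Conclusion.** The concern holds as a conflict between sections that permits, but does not make certain, informative censoring of PFS and OS. Its size depends on how often 6.9 is used and for whom, which the documents do not say. Under the stated assumptions it is about 3 points of 12-month OS for each early death censored a month beforehand, against a sampling SD of about 10 points. The direction is upwards if those withdrawn have a worse outlook than those who remain; withdrawals unrelated to prognosis would cost precision only. The same reasoning applies to PFS, for which no figure was calculated.

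The effect on the primary endpoint is small and limited to withdrawals for violation, administrative reasons or PI decision within the DLT window. The documents do not support reading 6.9 as ending every form of safety observation, or as showing that patients will in fact be lost for reasons linked to outcome. The point merits correction because the remedy is cheap and each patient is 4.2% of the maximum sample.

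**What to change.** Reconcile 6.9 with 6.8.1 and 3.4.3:

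- Limit withdrawal from study assessments to withdrawal of consent to follow-up or loss to follow-up. Treat death as an outcome, not as a withdrawal.
- State that, after any investigator or Sponsor decision to end treatment, the following continue unless the patient withdraws consent to them: AE recording to the safety visit, toxicity assessment to the end of the DLT window, disease assessment, and 12-weekly survival contact.
- Leave the replacement rule in 4.3 as it is. Making these patients non-replaceable could force someone with little pembrolizumab after SBRT into the DLT-evaluable set, since cycles 2 to 5 fall within the window. That would tend to understate the toxicity of the combination.

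The cost is protocol wording and a few extra follow-up contacts. Survival contacts can be made from the notes, by telephone or through the GP, as 3.4.3 and 5.1 already provide. Sample size and analysis methods do not change.

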## 7 PHARMACOVIGILANCE

---

### 7.1 Adverse events

#### 7.1.1 Adverse Event Definition

An AE is defined as any untoward undesired or unplanned occurrence (including deterioration of a pre-existing medical condition) in a patient administered a pharmaceutical product or undertaking a protocol-specified procedure. An AE can therefore be any unfavourable and unintended sign symptom, or disease and/or laboratory or physiological observation associated with the use of a medicinal product or protocol-specified procedure but does not necessarily have to have a causal relationship to this treatment or procedure. Any worsening (i.e. any clinically significant adverse change in frequency and/or intensity) of a pre-existing condition that is temporally associated with the use of pembrolizumab, is also an AE. Changes resulting from normal growth and development that do not vary significantly in frequency or severity from expected levels are not to be considered AEs. Examples of this may include, but are not limited to, onset of menses or menopause occurring at a physiologically appropriate time. AEs may also occur in screened patients during any pre-allocation baseline period as a result of a protocol-specified intervention, including washout or discontinuation of usual therapy, diet, placebo treatment or a procedure.

#### 7.1.2 Adverse Reaction Definition

An AE assessed by the Principal Investigator and / or Chief Investigator as reasonably likely to be related to the administration of a medicinal product or protocol-specified procedure.

#### 7.1.3 Disease Progression

Disease progression of the cancer under study is not considered an AE unless it results in hospitalisation.

#### 7.1.4 New Cancers

The development of a new cancer should be regarded as an SAE and reported accordingly.

#### 7.1.5 Abnormal Laboratory Test Results

All clinically important abnormal laboratory test results occurring during the study will be recorded as AEs. The clinically important abnormal laboratory tests will be repeated at appropriate intervals until they return either to baseline or to a level deemed acceptable by the investigator, or until a diagnosis that explains them is made.

#### 7.1.6 Pregnancy and Lactation

Pregnancy and lactation are not considered AEs, however these events should be reported to the RM-CTU following guidance in section 7.7

## 7.2 Assessing and Recording Adverse Events

All AEs will be recorded from the time of the first dose until the safety follow-up in the CRF. They will be followed up according to local practice until the event has stabilised or resolved, or the follow-up visit has taken place, whichever is the sooner. SAEs will also be recorded throughout the study. The reporting timeframe for AEs meeting any serious criteria is described in section 7.4.1.

Follow-up of AEs with a causality of possible, probable or highly probable will continue until the events resolve, stabilise or the patient completes the trial. Any unresolved AEs at the patient's last visit should be followed up for as long as medically indicated, but without further recording in the CRF.

If an Investigator learns of any AE that he/she consider serious, including death, at any time after a patient has completed the study and he/she considers there is a reasonable possibility that the event is related to pembrolizumab, the Investigator should notify the RM-CTU. Late toxicities will be recorded and reported as with other AEs.

The following details will be collected in the CRF for each AE:

- AE description / diagnosis
- Date of onset and date of resolution
- NCI-CTCAE grade maximum intensity
- Seriousness
- Investigator causality rating against the study medication (yes or no)
- Expectedness
- Action taken with regard to study medication
- Outcome

For the pre-registration period AEs will not be collected in patients that have not undergone any protocol-specified procedure or intervention. If the patient requires a blood draw, fresh tumour biopsy etc. for the study then the patient will be required to consent to the main study and AEs will be captured as described above.

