### **2.2.2 Secondary Endpoints**

- To assess the rates of acute toxicity (defined as up to 12 weeks after the last fraction of stereotactic radiotherapy) using CTC AE v4.0.
- To assess the rates of late toxicity (defined as from 12 weeks after last fraction of lung SBRT until 28 days after the last dose of pembrolizumab) using CTCAE version 4.0.
- To calculate the ORR and DCR using RECIST v1.1 & irRC.
- To calculate the ORR and DCR in squamous versus non-squamous histological subtype using RECIST v1.1 & irRC.
- To assess the frequency of PD-1/PD-L1 expression distribution in responders and non-responders.
- To measure the PFS and OS at 6 and 12 months.

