In the dose escalation phase, a minimum of 3 patients will be required per dose level being assessed. A minimum gap of 1 week will be left between the treatment of the first and the second, and between the second and the third patients with the combination of pembrolizumab and lung SBRT to mitigate against multiple patients suffering from acute toxicity. The DLT period for this study is 12 weeks from the last dose of lung SBRT (i.e. at C6D1). The dose escalation will be considered by the Safety Review Committee (SRC) once the 3rd or 6th patient in the cohort has completed the DLT period. If no DLT is observed at a dose level,

then lung SBRT will be dose escalated to the next dosing level (see Table 1). If 1 out of 3 patients experience a DLT, then the cohort will be expanded to 6 patients. If 1 in 6 patients experience a DLT, then the dose will be escalated to the next dosing level. However, if  $\geq 2$  in 6 patients experience a DLT then the maximum administered dose (MAD) will have been reached, and the RP2D will be the previous dosing level that will be used for the dose expansion cohorts. If the MAD is seen at dose level 1 then the study will be terminated. While waiting for 3 or 6 patients to complete the DLT period, no additional patients will be recruited. Further patients can only be recruited after the SRC has reviewed the toxicity data for the cohort and taken a decision to dose escalate to the next cohort or expand the current cohort to 6 patients.

Once the MTD has been determined the trial enters the dose expansion phase (unless the MTD is dose level 1). Here, 12 patients will be treated with the RP2D of SBRT combined with pembrolizumab.

If there is ongoing clinical benefit at 24 months, the CI/PI will need to discuss with the sponsor and MSD, on a case by case basis for the continuation of pembrolizumab.

**Table 1:** Lung SBRT dose levels and pembrolizumab dosing during the dose escalation and dose expansion phase.

Dose Level	Pembrolizumab Dose	Lung SBRT to part of a lung lesion
1	200 mg i.v. over 30 minutes, every 3 weeks	30 Gy in 3# (Monday, Wednesday, Friday)
2	200 mg i.v. over 30 minutes, every 3 weeks	54 Gy in 3# (Monday, Wednesday, Friday)
Dose expansion	200 mg i.v. over 30 minutes, every 3 weeks	RP2D

SBRT: Stereotactic Ablative Body Radiotherapy; Gy: Gray; i.v.: intravenous; mg: milligrams;  
RP2D: Recommended Phase 2 Dose; #: fraction.

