### **3.4 Follow-Up after stopping Pembrolizumab**

#### **3.4.1 30 Day Safety Follow-Up Visit**

All patients will be required to attend a safety follow-up visit 30 days after the last dose of pembrolizumab or before the initiation of a new anti-cancer treatment, whichever comes first. All adverse events (AEs) and serious adverse events (SAEs) that occur prior to the safety follow-up visit should be reported as described in section 7. After the safety follow-up any unresolved AEs at the patient's last visit should be followed up for as long as medically indicated, but without further recording in the CRF.

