### **5.3.2 Adverse Event (AE) Monitoring**

The investigator or qualified designee will assess each patient for potential new or worsening AEs as specified in the schedule of study assessments (Table 3) and more frequently if clinically indicated. AEs will be graded and recorded from confirmation of entry into the trial until the patients 30 day safety follow up visit according to NCI CTCAE v4.0 (see Appendix 4). Toxicities will be characterised in terms regarding seriousness, causality, toxicity grading, and action taken with regard to trial treatment.

All AEs of unknown aetiology associated with pembrolizumab exposure should be evaluated to determine if it is possibly an event of clinical interest (ECI) or a potentially an immune-related adverse event (irAE). See Appendix 5 and the separate ECI guidance document regarding the identification, evaluation and management of AEs of a potential immunological aetiology. Please refer to section 7 for detailed information regarding the assessment and recording of AEs.

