Patients who in the assessment by the investigator, require the use of any of the aforementioned for their clinical management should be removed from the trial. Patients may receive other medications that the investigator deems to be medically necessary. The Exclusion Criteria describes other medications which are prohibited in this trial. There are no prohibited therapies during the Post-Treatment Follow-up Phase.

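### For patients whose last pembrolizumab dose is cycle 4 or earlier, or who start new therapy early, routine AE recording can stop before the 12-week post-SBRT window closes

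*Combined protocol and SAP*

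**What the plan says.** **Recording follows pembrolizumab.** Section 7.2: "All AEs will be recorded from the time of the first dose until the safety follow-up in the CRF". Section 5.3.2 agrees, with AEs graded and recorded "until the patients 30 day safety follow up visit according to NCI CTCAE v4.0". Section 3.4.1 defines the visit as "a safety follow-up visit 30 days after the last dose of pembrolizumab or before the initiation of a new anti-cancer treatment, whichever comes first", and adds that AEs still unresolved afterwards are followed clinically but no longer entered in the CRF. Section 6.8.1 repeats the same stopping point.

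**The safety windows follow SBRT.** Section 3.2: "The DLT period for this study is 12 weeks from the last dose of lung SBRT (i.e. at C6D1". Section 2.2.2 sets the secondary endpoint as "acute toxicity (defined as up to 12 weeks after the last fraction of stereotactic radiotherapy". Neither definition makes an exception for patients who stop pembrolizumab early.

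**Who is counted.** Under section 4.3, a patient who leaves for progression within 3 months of radiotherapy is not evaluable for DLT and is replaced. One lost for reasons other than progression or toxicity may be replaced. For the third group: "A patient that discontinues the trial for a drug-related AE will not be replaced and will be counted in the evaluable population of patients". Section 8.1.2 analyses secondary endpoints, including acute toxicity, in all Part A and Part B patients.

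**The concern.** Toxicity from an SBRT dose already given does not stop when pembrolizumab stops. If recording ends first, non-serious events in the remaining weeks may never reach the CRF, while the patient stays in the acute-toxicity denominator. The observed rate can then only be too low. The patients with shortened observation are also not a random subset, since they are the ones progressing or already having toxicity.

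For the primary endpoint, each dose level rests on 3 to 6 patients, and 1 of 6 against 2 of 6 decides escalation. A single evaluable patient without full observation therefore matters, although few patients can fall into that position.

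**Working it through.** **1. The plan's own window.** The last fraction is on C1D19 (section 3.2), so 12 weeks end on day 19 + 84 = 103. With 21-day cycles, C6D1 is day 1 + 5 × 21 = 106. The two differ by 3 days, which the ±3-day visit allowance covers, so the plan's figure reproduces.

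**2. The gap.** Recording ends on day (last dose + 30). Gap = 103 − (last dose + 30).

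| Last dose | Day | Recording ends | Gap (days) | Share of 84 days |
|---|---|---|---|---|
| C1 | 1 | 31 | 72 | 86% |
| C2 | 22 | 52 | 51 | 61% |
| C3 | 43 | 73 | 30 | 36% |
| C4 | 64 | 94 | 9 | 11% |
| C5 | 85 | 115 | 0 | 0% |

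If a ±7-day allowance applies to the safety visit, the C4 gap is 2 to 16 days. If new therapy starts before the 30-day point and before day 103, the gap is 103 minus its start day, whatever the last dose.

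**3. How many patients, for acute toxicity.** The protocol gives no figure, so this is an assumption: exponential PFS with the medians of 3.0 to 4.0 months cited in section 1.1.4.2. P(progressed by day t) = 1 − 0.5^[(t − 1)/30.44/median].

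- Progression found at the week-9 scan (day 64), last dose C3: 1 − 0.5^(2.07/3.0) = 38%, and 1 − 0.5^(2.07/4.0) = 30%. That is 7 to 9 of 24.
- Stopping at first progression whenever it occurs, last dose C4 or earlier (progression by day 85): 1 − 0.5^(2.76/3.0) = 47%, and 1 − 0.5^(2.76/4.0) = 38%. That is 9 to 11 of 24.
- Clinically stable patients treated until a confirmatory scan at least 4 weeks later (section 5.3.11.3): 64 + 28 = day 92, after C5 on day 85. They have no gap unless new therapy starts before day 103.

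**4. The DLT route.** Section 4.3 keeps drug-related-AE stoppers evaluable without requiring 12 weeks of observation. Such patients can arise: recurrent grade 2 pneumonitis leads to permanent discontinuation in Table 8 but lies below the grade 3 DLT threshold in section 3.2.1.

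P(escalate) = P(0 of 3) + P(1 of 3) × P(0 of next 3). At an illustrative true DLT rate of 0.33, this is 0.3008 + 0.4444 × 0.3008 = 0.434. Suppose one retained patient among the first three has gap g, DLT timing is even, and nothing is captured in the gap. That patient's detectable rate is 0.33 × (1 − g/84), and P(escalate) becomes 0.450, 0.487, 0.524 or 0.561 for g = 9, 30, 51 or 72.

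Section 1.1.4.2 cites 4–5% discontinuation for related AEs on pembrolizumab alone. The chance of at least one such patient among three is 1 − 0.96³ = 12% to 1 − 0.95³ = 14%. The unconditional shift is then roughly 0.115 × 0.016 = 0.2 to 0.143 × 0.127 = 1.8 percentage points. The 4–5% covers the whole treatment course and all related AEs, including any that would be DLTs. The rate for the combination is unknown.

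**5. Could the 9-weekly visits fill the gap?** Counted from the safety visit (+63 days), the first falls on day 94, 115, 136 or 157 for a last dose at C1 to C4. Only the C1 case lies inside the window. For the others, events could only be collected in retrospect.

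**The case against.** A reader might infer that early stoppers in general are scored DLT-free over weeks in which nobody recorded anything. The documents do not support that.

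- **Progression.** Section 4.3 makes these patients non-evaluable for DLT and replaces them, and it allows replacement for other non-toxicity reasons. What remains is drug-related-AE stoppers and optional replacements that are not made. Most permanent-discontinuation triggers in Table 8 are grade 3–4 events that would generally be DLTs anyway.
- **Other recording.** Section 7.2 also says SAEs are recorded throughout the study. Section 7.4.1 keeps SAEs related to the drug or a protocol procedure reportable at any later time. Section 3.2.1 says acute toxicity is assessed to 3 months after radiotherapy. The AE row of Table 3 appears to reach the 9-weekly visits, although the table is broken in the text available and the alignment is inferred.
- **Analysis.** Section 8.1 describes separately patients who did not complete the safety observations required of them.
- **New therapy.** Stopping collection there limits confounding.

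These points narrow the concern but do not remove it. Routine SAE reporting in 7.4.1 ends at the same 30-day or new-therapy point, and later reports depend on an event reaching the investigator. A grade 3 oesophagitis lasting more than 7 days can be a DLT without being an SAE. The sentence in 7.2 on late toxicities does not help, because section 2.2.2 starts late toxicity only at 12 weeks. Section 3.2.1 and Table 3 conflict with 3.4.1, 5.3.2 and 7.2, and survival follow-up appears to have no AE mark. Section 8.1 does not say which observations are required.

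A reader might also infer a second route from section 6.3.1: patients who "require the use of any of the aforementioned for their clinical management should be removed from the trial" could include those needing steroids for a purely radiation-induced event. This is speculative. The same section elsewhere says such patients may be discontinued, section 7.5.1 presumes an immune cause when no other is found, and the prompting event would already be recorded. The wording within 6.3.1 should be reconciled, but it adds no established loss of data.

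**Conclusion.** The point holds in limited form and should be fixed as a cheap improvement. Routine recording of non-serious AEs can end 9 to 72 days before the 12-week window closes for a last dose at C4 to C1, or earlier if new therapy starts sooner. That much is calendar arithmetic from the protocol.

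The main consequence is possible under-ascertainment of acute toxicity, since all patients are analysed and no rule covers incomplete windows. The figure of 7 to 9 of 24 (up to 11 if patients stop at first progression) assumes exponential PFS at the cited medians and no treatment beyond first progression. It falls, possibly a long way, if stable patients continue until confirmation.

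For DLTs the exposure is narrow. The effect on escalation is material only if a retained AE-stopper is in the cohort: from 0.434 to between 0.450 and 0.561 in the illustration. On average it is small, at about 0.2 to 1.8 percentage points under the monotherapy discontinuation rate. The documents do not support a claim that the primary endpoint is broadly biased.

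**What to change.** - **Sections 3.4.1, 5.3.2, 7.2, 7.4.1 and Table 3:** record AEs and SAEs until the later of the 30-day safety visit and 12 weeks after the last SBRT fraction, regardless of pembrolizumab discontinuation, progression or new therapy. Record new-therapy start dates so that confounded events can be flagged. Align 6.8.1, which carries the same stop.
- **Section 4.3:** count a patient as DLT-free only if observed for the full 12 weeks. A patient without a DLT who was not observed that long is not evaluable. Extended recording should keep that group small, which matters because dropping AE-stoppers would itself be selective.
- **Section 8.1.2:** report how many patients have an incomplete acute window.

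Under the recording rule the gap becomes 0 days for every last dose, and the planned maximum of 24 is unchanged. The cost is protocol wording, one or two clinic or telephone AE checks per early stopper, and some AEs confounded by new therapy.
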